7.4. Rescue Medications

Treatment of individual allergic reactions during OIT therapy should be with either an antihistamine and/or epinephrine, along with IV fluids, albuterol and steroids as indicated. Subjects and parents are likely to already have EpiPens[®], but for those who do not, a prescription for EpiPens[®] (or equivalent device) will be provided. Subjects and parents will be trained in proper use and will be able to demonstrate proper technique with the EpiPen[®] (or equivalent device).

8. Study Procedures

8.1. Enrollment

The research study will be explained in lay terms to each potential research participant. The potential participant will sign an informed consent form before undergoing any study procedures. Participants will be considered enrolled into the study and assigned a unique study identification number after signing the informed consent/assent document(s).

8.2. Screening/Baseline Visit

The purpose of the screening period is to confirm eligibility to continue in the study. The Screening/Baseline assessments may take place over several visits. Baseline/screening visits following requirements below, conducted under a different protocol (Screening Protocol) can be used towards this study.

All assessments must be completed no more than 40 weeks (Appendix 1) preceding initiation of FA treatment.

The following procedures, assessments, and laboratory measures will be conducted to determine participant eligibility:

- Consent and assent
- Medical history, including review of all food allergies
- Review of medications participants are currently taking
- Physical assessment
- Pregnancy test, if subject is a female who has undergone menarche and is of childbearing potential (i.e., not otherwise incapable of having children from a previous medical condition, surgery, or other circumstance)
- Blood draw for allergen-specific IgE and IgG4 measurement, lab tests and research samples
- Skin prick test to FA extract (neat extract with no dilution, Greer Laboratories, Lenoir, NC)
- Spirometry and/or Peak Expiratory Flow (PEF)
- Stool sample collection
- DBPCFC to a 443 mg cumulative total allergen protein

Any of the above items may be repeated within the 40 weeks preceding initiation of study treatment if warranted, in the opinion of the investigator, by changes in the subject's clinical status.

Double-Blind Placebo-Controlled Food Challenge (DBPCFC) at Screening

Randomization and preparation of the challenge materials will be performed by trained study personnel in the GMP facility at Stanford. Prior to the food challenge, subjects will be asked to restrict the use of oral antihistamines (five half-lives), beta-agonists (12 hours), theophylline (12 hours), and cromolyn (12 hours).

Subjects will not have active wheezing, spirometry demonstrating FEV1 <80% predicted, or a current flare of atopic dermatitis that contraindicates dosing in the clinical judgment of the study physician. If the participant is unable to perform spirometry, a peak expiratory flow \geq 80% predicted and clear breath sounds on a lung examination will be used to determine if an oral food challenge can be performed.

The screening DBPCFC will consist of doses given every 15-30 minutes in increasing amounts up to a cumulative total of 443 mg of allergen protein. If the study team suspects a reaction may be developing, they may exercise their clinical judgment to separate doses by up to an additional 30 minutes (one hour maximum between doses). The other challenge will consist of placebo material given also in an equal number of doses. The doses will be 3 mg, 10 mg, 30 mg, 100 mg and 300 mg modified PRACTALL dosing by Sampson et al, JACI 2012; [https://www.jacionline.org/article/S0091-6749\(12\)01663-6/pdf](https://www.jacionline.org/article/S0091-6749(12)01663-6/pdf)) Before each challenge, the subject will have a physical assessment administered by a trained physician's assistant, registered nurse, nurse practitioner, and/or physician of the study team who is blinded to the testing material. The supervising investigator will also be blinded to testing material.

The food challenge will be stopped based on dose limiting symptoms defined in Appendix 3. If the subject begins to have any objective symptoms or subjective symptoms deemed clinically significant, the food challenge will be terminated, and the subject will be given appropriate treatment. The subject will be observed for a minimum of two hours after the final administered dose and discharged only when deemed clinically stable by a study physician. All food challenges will be performed under physician supervision. If the subject has no symptoms related to allergic reactions to the food allergen ingestion with the DBPCFC at or before 443 mg, they will not be enrolled in the study.

8.3. Study Visits or Study Assessments**Allergen-Specific OIT Treatment Overview**

Food allergen OIT administration will include an Initial dose day (IDD) with oral immunotherapy dosing beginning at 5 mg occurring in the Stanford SNP-CRU.

A targeted history and physical assessment will be performed at each in person visit. Physical assessments performed in this protocol will be allergy focused and include the following systems: head and neck, including thyroid; eyes, ears, nose, and throat; lungs; heart; abdomen; and skin. Subjects will be assessed for exacerbation of atopic dermatitis or asthma (as determined by active wheezing or report of an increased need for rescue medication in the prior week) prior to each in-SNP-CRU dosing. In the presence of an exacerbation of atopic dermatitis, the study physician will use their professional judgment in deciding whether the exacerbation should preclude an attempt at up dosing. In the presence of wheezing in any child, regardless of asthma history, spirometry (per manual of procedures) will be performed to assess FEV1. If FEV1 <80% predicted value, bronchodilators will be administered, and spirometry will be repeated. If FEV1 \geq 80% predicted value (with or without bronchodilator administration) the updose may be attempted in SNP-CRU. If FEV1 <80% predicted value after bronchodilator administration, the participant will remain at their current dose for two additional weeks. That day's dose should be administered either in SNP-CRU and monitored as an updose.

In addition to dosing visits, subjects will return to the SNP-CRU at designated visits (see Appendix 1) for their OFC or other assessments/blood draws. A medical and diary review, and targeted physical assessment will also be performed at these visits. OFCs will occur at screening, end of maintenance phase (Week 52), end of withdrawal phase at Week 58 and at Week 64 if opted for by the participant.

After subjects have met the criteria outlined above (Section 3.1), medical history, diet history, spirometry, SPT, and a physical assessment will be performed.

Allergen-Specific OIT:

Initial Dose Day (Day 1) – The Initial Dose Day will be done at the SNP-CRU and consist of either cashew or shrimp OIT dosing. Subjects will not have active wheezing, spirometry demonstrating FEV1 <80% predicted, or a current flare of atopic dermatitis that contraindicates dosing in the clinical judgment of the study physician. If the participant is unable to perform spirometry, a peak expiratory flow > 80% predicted and clear breath sounds on a lung examination will be used to determine if a dose escalation can be performed. A physician will be present at all times during any of the SNP-CRU food allergen OIT dosing visits and will be available to respond within 60 seconds to any allergic reaction. Subjects tolerating the 5 mg single dose will remain on that daily dose for 2 weeks. They will then return every 2 weeks to the SNP-CRU for single updose.

Updosing Phase (Build-up Phase) (Week 2-28): Subjects will receive subsequent doses (**Table 2**) at home for the next 14 days. Subjects* who do not tolerate the 5 mg dose will be given 3 mg daily and return in about 7 days for updosing to 5 mg before proceeding to next dose. Subjects will be instructed to continue dietary food allergen (cashew or shrimp) avoidance throughout the entire study. They will also be instructed not to introduce any new foods to the diet and to continue avoidance of the subject's other known food allergens, if any. At 2-week intervals, the subjects will return for a possible increase in the daily oral dose until they reach 1000 mg FA protein build-up phase. During dose escalation, there should be increased hydration (i.e. about 16 oz or more given orally for an adult and an adjusted volume for children based on size) and restricted exercise for 2 hours after dosing.

Table 2: Daily FA Protein Dosing and Increase Schedule for Build-Up Phase

Dose #	Dose	Interval (Weeks)	% of Increase
1	5 mg*	2	Initial dose day
2	7.5 mg	2	50%
3	15 mg	2	100%
4	30 mg	2	100%
5	50 mg	2	67%
6	75 mg	2	50%
7	100 mg	2	33%
8	150 mg	2	50%
9	200 mg	2	33%
10	300 mg	2	50%
11	400 mg	2	33%
12	550 mg	2	38%
13	700 mg	2	28%
14	1000 mg	2	36%

*: Note: Participants may return a second time within a period of a week to be given 5 mg. The criteria to be given it again will be if there is a moderate reaction (as per CoFAR criteria) on the first attempt.

Subjects will begin the SNP-CRU dosing schedule as outlined above until 1000 mg of FA protein is reached. Any uposing attempts may be postponed for 1-2 extra visits based on clinical judgment. However, an uposing attempt must be made within a maximum of 3 consecutive scheduled clinic visits. Subjects should withhold their daily home dose and any prophylactic antihistamines on the in-SNP-CRU uposing day but should take all other prescribed medications. Note that the daily home dose should be taken as part of a meal at a consistent time (within 24±2 hours of the previous day's dose), and it is critical to take the dose every day. Doses should be separated by at least 12 hours. Subjects who require dosing reduction by 50% during the 2-week period due to illness will undergo an attempted uposing only after resuming their full dose for a minimum 3 days.

If participants miss a dose and remember less than 12 hours from when they were supposed to take that dose, participants may take the dose and resume the next dose on schedule. If they are within 12 hours of the next dose, they should not take the missed dose, but wait and take the next scheduled dose at the usual time (or if they miss a dose by more than 12 hours, they should contact study personnel to receive instructions on how to proceed).

As stated above, an uposing attempt must be made within 3 clinic visits on a given dose, unless uposing is delayed due to administration of epinephrine as defined in Section 6.4.3 or illness. If the subject fails to successfully increase uposing for three consecutive attempts, uposing will be halted at the last tolerated dose. Please refer to the Participant Disposition (Appendix 2) for follow up depending on the dose tolerated.

Vigorous exercise is not permitted for at least 2 hours after the dose of oral allergen immunotherapy. Also, there must be at least 1 hour between vigorous exercise and taking a dose of oral allergen immunotherapy. Allergic reactions are still possible when exercise takes place more than 2 hours after the dose.

Should significant systemic symptoms, which may include mild symptoms based on physician discretion or moderate or greater symptoms, be reported during the daily home dosing, the symptom/dosing algorithm will be followed to determine the best course of action. The appropriate treatment will depend on the type and number of symptoms. Subjects will be allowed to take their other daily medications during the build-up and maintenance phases of the study (i.e., antihistamines, albuterol) except where prohibited in this protocol.

In the event of an epidemic/pandemic or other unforeseen circumstances during which the patient cannot come into clinic, we will plan on sending doses to their homes/residences, and/or perform home visits or telehealth visits. Subjects may be maintained on the previously tolerated dose until a dose-escalation can be performed safely.

Maintenance Phase (Week 28-52): Subjects will undergo uposing until reaching a daily maintenance dose of 1000 mg and they will remain at that dose and return for follow-up visit at Week 52. Based on our previous data using a similar dosing method (Table 2), we expect all subjects on active treatment to reach 1000 mg between the Week 28 and Week 52 visits.

On Study DBPCFC (Week 52): At Week 52 all subjects will have a DBPCFC to up to 4043 mg to assess desensitization. The visit will also include a physical assessment, spirometry and/or PEF, stool sample collection and blood draw for allergy tests and mechanistic studies.

The subject's sensitivity to food allergen is defined as the dose at which the subject experiences allergic reactions. All symptoms and signs will be evaluated and rated based on a standardized oral food challenge scoring system (CoFAR guidelines, Appendix 3). During the oral food challenge, there should be increased hydration (i.e. about 16 oz or more orally).

Uposing during the DBPCFC will be stopped when the Principal Investigator (or designee) finds symptoms and/or signs that indicate a definite allergic reaction (CoFAR guidelines) has occurred based on clinically significant changes in reported symptoms, physical findings, or vital signs that the subject is experiencing to the challenge material. The challenge will consist of doses based on modified PRACTALL guidelines and will include 3mg, 10mg, 30mg, 100mg, OIT in Shrimp or Cashew allergy (MOTIF protocol) Version 4.0 26MAY2022

300mg, 600mg, 1000mg and 2000mg. . Both food allergens (cashew or shrimp) and oat protein will be concealed in a food that masks the taste. After the last dose of the DBPCFC, the subject will be monitored for 2 hours and then discharged home. Subjects will be considered to have tolerated the OFC if they do not experience any objective reactions by Appendix aa.

If the subject experiences reactions, they will be treated with the necessary rescue medications. They will be observed for a minimum two hours after the final administered dose and discharged home only when deemed clinically stable by a study physician.

After the Week 52 DBPCFC, subjects who meet the following criteria will discontinue FA protein daily dosing entirely:

- On OIT treatment for 52 weeks,
- Taking daily maintenance dose of 1000 mg protein for approximately 3 weeks,
- No severe reactions (CoFAR criteria) to home dosing, and/or

Subjects who do not pass a cumulative of 2043 mg at Week 52 will be considered desensitization failures. They will be considered in statistical analyses of the intent-to-treat population. They will be followed until the end of study (week 58).

After Week 52, all subjects will begin their withdrawal phase for 6 weeks.

On Study DBPCFC (Week 58, Week 64): At Week 58 subjects will have a DBPCFC to up to 4043 mg to assess sustained unresponsiveness (tolerance). The visit will also include a physical assessment, spirometry, fecal matter collection, skin prick test, and blood draw for mechanistic studies.

During the oral food challenge, there should be increased hydration (i.e. about 16 oz or more given orally). There are no published data indicating whether repeating food challenges every 6 weeks will or will not maintain desensitization or otherwise affect the outcomes in this study. Our preliminary studies in which we have performed DBPCFCs every 3 months in a separate phase 1 study cohort (n=87 subjects) have demonstrated no increased risk of sensitization (as per repeat cumulative doses on repeat DBPCFC and as per severity of reaction).

End of study (Week 58 or Week 64): Participants will be followed until week 58 or until Week 64 if they opt to continue avoidance of OIT for 8 more weeks after Week 58.

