6.4.2 Reactions to OIT During build-up or Maintenance Phase

To be able to be eligible for an updosing or maintenance dose visit, subjects cannot have active wheezing, spirometry demonstrating FEV1 < 80% predicted and/or Peak Expiratory Flow (PEF) < 80% predicted or a current flare of atopic dermatitis that contraindicates updosing in the clinical judgment of the study physician. As needed, subjects will be maintained on their current dose of study product until their flare of asthma or atopic dermatitis is resolved.

If a subject has an updosing in the SNP-CRU without symptoms, the action should be to continue per protocol with daily home dosing of the tolerated dose with the next updosing visit 2 weeks later.

If the subject only experiences *oral/pharyngeal pruritus* during the administration of the daily dose, then the same dose can be repeated the next day at home and continued throughout the interval unless other symptoms begin to develop.

For other *mild objective symptoms* (Appendix 3), the action should be either to repeat the dose the next day (day 2) at home or to have the subject return to the SNP-CRU the next day (day 2) for a repeat of the previous day's dose or the last tolerated dose (at the study physician's discretion). If the dose is tolerated, then the subject will continue on that dose and return at the normal interval. If the dose causes mild symptoms again, then the subject may return to the SNP-CRU the next day (day 3) and be given the last tolerated dose or a 1-2 step dose reduction. If tolerated, the subject will continue on this dose for the normal time interval. If mild symptoms recur, a 1-2 step reduction should be administered the next day (day 4). If tolerated, then that dose should be continued for 2 weeks. If not tolerated, consultation with the PI is indicated.

If *moderate symptoms* (Grade 2, Appendix 3) occur, the action should be to have the subject return to the SNP-CRU the next day (day 2) for dosing with the previous days dose or the last tolerated dose, at study physician discretion, under OIT in Shrimp or Cashew allergy (MOTIF protocol) Version 4.0 26MAY2022

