For specific questions related to dosing escalation or continuation of the same dose that are not answered in the above protocol, the PI will be available for questions and decision-making.

If, at any point in the study, the subject complains of new onset vomiting, dysphagia, chronic abdominal pain, and/or difficulty swallowing for more than 2 weeks despite use of daily anti acids (<https://www.webmd.com/heartburn-gerd/qa/what-are-examples-of-antacids>), the subject will be given daily proton pump inhibitors (dosed per age and weight) <https://medlineplus.gov/ency/patientinstructions/000381.html> and if no relief occurs in 2 weeks, they will be referred to a gastroenterologist for assessment of possible gastroenterological disorders associated with food allergy (i.e., eosinophilic esophagitis). If at any point, side effects develop from the use of antacids or PPIs, the subject will be discontinued for the concomitant medication and referred to a GI specialist.

Any subject who discontinues build-up dosing due to repeated allergic reactions to the characterized food allergen will have his/her blood drawn for mechanistic studies within approximately 1 week of discontinuation of therapy.

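### Section 6.4.2 bars an updosing visit for any subject who is wheezing, but Section 8.3 lets a wheezing child be updosed once FEV1 is at least 80% predicted, and neither rule is given precedence

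*Combined protocol and SAP*

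**What the plan says.** **Section 6.4.2** sets the eligibility rule for dosing visits: "To be able to be eligible for an updosing or maintenance dose visit, subjects cannot have active wheezing". FEV1 and/or peak flow below 80% predicted is a separate item in the same list. So is an atopic dermatitis flare, and the study physician's clinical judgment is attached to that item only. The section then says: "As needed, subjects will be maintained on their current dose of study product until their flare of asthma or atopic dermatitis is resolved".

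**Section 8.3 (Allergen-Specific OIT Treatment Overview)** gives a different pathway. It treats active wheezing as a marker of asthma exacerbation, to be checked before each in-clinic dosing. It continues: "In the presence of wheezing in any child, regardless of asthma history, spirometry" is performed. A bronchodilator is given only if FEV1 is below 80% predicted. For FEV1 at or above 80% "predicted value (with or without bronchodilator administration) the updose may be attempted in SNP-CRU". The dose is held, for two more weeks, only if FEV1 is still below 80% after the bronchodilator.

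**Parallel rules.** The screening challenge (8.2) and the Initial Dose Day (8.3) each exclude active wheezing as well as FEV1 below 80%. Where peak flow replaces spirometry, both also ask for clear breath sounds.

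**The concern.** The two sections govern the same event, an in-clinic updosing visit, and answer the same question differently for an identifiable child. Two study physicians could each follow the protocol and act in opposite ways.

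Three things are at stake.

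- **Safety.** The dose is an allergen that can itself provoke wheeze and anaphylaxis (5.2, 5.3). Computed from the doses listed in Table 2, each step raises the daily amount by between 27% (550 to 700 mg) and 100% (7.5 to 15 mg, and 15 to 30 mg).
- **Judging tolerance.** Appendix 3 classes wheezing even without dyspnea as moderate, and all moderate symptoms as dose-limiting. If the child was wheezing before the dose, whether the dose was tolerated cannot be judged cleanly.
- **Deviation reporting.** Section 15.1 permits no departures from the protocol. An updose in this child complies with 8.3 and deviates from 6.4.2, so neither staff nor monitors can tell whether to report it.

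**Working it through.** No arithmetic bears on whether the conflict exists. The check is to apply both rules to each possible state at an updosing visit.

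| State at the visit | Section 6.4.2 | Section 8.3 | Result |
|---|---|---|---|
| Child wheezing, FEV1 at least 80%, no bronchodilator given | Ineligible (wheeze) | Updose may be attempted | Conflict |
| Child wheezing, FEV1 below 80%, rises to at least 80% after bronchodilator, wheeze persists | Ineligible (wheeze) | Updose may be attempted | Conflict |
| As above, but wheeze clears | Does not say whether the later FEV1 counts | Updose may be attempted | Ambiguity only |
| Child wheezing, FEV1 still below 80% after bronchodilator | Ineligible | Held two more weeks | Agree |
| Atopic dermatitis flare | Physician judgment | Physician judgment | Agree |
| Adult wheezing, any FEV1 | Ineligible | No pathway given | No conflict |

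The first row is the plainest case. A child wheezing with FEV1 of, say, 85% predicted is barred by 6.4.2. Under 8.3 the same child may be updosed without treatment, because the bronchodilator step is reached only below 80%.

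Three readings might reconcile the sections:

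1. *The clinical-judgment phrase in 6.4.2 covers wheeze.* By its position and wording it belongs to the atopic dermatitis flare.
2. *Section 8.3 is a child-specific exception.* Neither section says so, and 6.4.2 speaks of subjects without exception. Section 6.4.2 refers to Appendix 3 and not to 8.3. Section 8.3 refers to Sections 3.1 and 6.4.3 and to appendices, and not to 6.4.2. This reading would also give the younger group the looser rule with no reason stated.
3. *FEV1 of at least 80% means the wheeze does not matter.* The screening and Initial Dose Day rules list the two criteria separately, so the protocol does not treat them as equivalent.

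The fallback to the PI in 6.4.2 does not settle it either. It is for "For specific questions related to dosing escalation or continuation of the same dose that are not answered in the above protocol", and this question is answered twice.

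**The case against.** The strongest reply is that both rules can be obeyed at once. Section 6.4.2 forbids and 8.3 only permits, so a physician who holds the dose breaches neither. That stands. A reader might infer that the protocol compels an unsafe updose, and the documents do not support this.

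A reader might also infer that the three-visit limit in 8.3 eventually forces the updose, since an "attempt must be made within a maximum of 3 consecutive scheduled clinic visits". The text does not bear that out. Updosing "may be postponed for 1-2 extra visits based on clinical judgment", and the limit is lifted when it "is delayed due to administration of epinephrine as defined in Section 6.4.3 or illness". An asthma flare plausibly counts as illness, and the hold in 6.4.2 runs until the flare is over. If asthma stays active or poorly controlled, the Synopsis and Section 6.5 already make that a ground for stopping OIT.

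Safeguards are substantial. Severe or uncontrolled asthma is excluded at entry (4.3). Updosing takes place in a hospital setting with a crash cart, a code team and standing orders for epinephrine (3.1). A physician is present and able to respond within 60 seconds (8.3). These limit the harm from a reaction, but none of them says which rule applies to the wheezing child.

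Finally, the sponsor may have intended 8.3 as the exception, and stating that in 6.4.2 would also remove the contradiction. The parallel rules favor the stricter reading, but they do not prove intent.

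**Conclusion.** The contradiction is real and narrow. It applies to a child who is still wheezing at an in-clinic updosing visit with FEV1 of at least 80% predicted, whether or not a bronchodilator was given. In that case following 8.3 as written permits an escalation that 6.4.2 bars. The textual finding rests on reading the clinical-judgment phrase in 6.4.2 as belonging to atopic dermatitis alone, which is its natural sense.

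The practical size is unknown. The documents give neither the share of children enrolled nor how often wheeze is found before dosing. A count of all scheduled updoses would say nothing about affected visits, so none is offered. No endpoint, power figure or analysis is touched. It should be corrected because it is a conflicting safety rule on allergen dosing in children and wording alone will cure it. There is no evidence here that participants have been or must be put at risk.

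**What to change.** Align 8.3 with the stricter rule by amending two sentences.

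- Permission: *If wheezing has resolved and FEV1 is ≥80% predicted, with or without a bronchodilator, an updose may be tried in the SNP-CRU.*
- Hold: *If wheezing persists, or FEV1 is <80% predicted after a bronchodilator, the current dose continues for at least two more weeks and until the flare has resolved, per Section 6.4.2.*

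Add a cross-reference to 8.3 in 6.4.2. This also settles that, once the wheeze has cleared, a post-bronchodilator FEV1 counts for a child. Tying the hold to resolution avoids a new mismatch with 6.4.2 over its length. The atopic dermatitis rule and the three-visit limit need no change. The 8.3 pathway remains for children only, so adults stay under 6.4.2 alone, as now.

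The cost is wording plus an occasional delay of two weeks or more. On Table 2, 1000 mg (dose 14) falls at 13 × 2 = week 26, so one two-week hold moves it to week 28, the planned date. With no other delay, each further two-week hold takes 2 weeks from the planned 52 − 28 = 24 weeks at 1000 mg. Section 3.1 already allows updosing to continue past week 28, up to week 52. If the sponsor prefers the looser rule, 6.4.2 should state the exception for children and give the reason.
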